	
 - Diabetes Treatment Satisfaction Questionnaire change (DTSQc), administered on Week 24 only - Hypoglycemia Fear Survey-II (HFS-II) - Diabetes Distress Scale (DDS) • HbA1c: change from baseline to Week 16 • FPG: change from baseline to Week 16 and Week 24 • Change in 7-point SMPG profiles, mean and per time-point from baseline to Week 16 and Week 24, • Insulin doses 
Patient care with the two approaches:
 
 • Study-specific resource requirements: Overall Study Experience-Sites (OSES) questionnaire part 1 (resource requirements) over the 24 week treatment period • Site-perceived patient relationship and satisfaction: OSES questionnaire part 2 at Week 24 • Patient interview in a subset of patients at Week 24 
Safety assessment managed by the two approaches:
 
 • Hypoglycemic events and incidence rate (as per the American Diabetes Association (ADA) classification) during the 24-week period in each group • Adverse events (including Injection site reactions and hypersensitivity), Serious AEs (SAEs) and Product Technical Complaints (PTCs)
ASSESSMENT SCHEDULE	See study flowchart in Section 1.2 .
STATISTICAL CONSIDERATIONS	
Sample size determination:
 
This is a pilot study, consequently no formal sample size calculation was done.
 
The sample size was not powered for confirmatory testing, only descriptive statistics will be provided.
 
Number of patients per trial approach group: randomization using a ratio 1 (virtual):1 (traditional).
 
Nevertheless, a precision calculation based on the 2-sided 95% confidence interval (CI) shows that the change in HbA1c from baseline in virtual approach, the change in HbA1c from baseline in traditional approach and the difference in HbA1c change between the two approaches will be estimated with a precision of approximately 0.37%, using a standard deviation (SD) of 1.1 and taking into account an up to 10% rate of non-evaluable patients for HbA1c.
 
General aspects of the analyses:
 
Except if defined below, the baseline value will be the last available value prior to the first injection of IMP.
 
Analysis population:
 
The primary population for all non-safety endpoints will be the Intent-To-Treat (ITT) population, which will comprise all randomized

[figure not shown]

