Injection site reactions, PTCs	To be assessed and reported (if any) since randomization throughout the study														
Central Laboratory^{k,e}															
HbA1c, FPG		X										X		X	
Hematology, clinical biochemistry ^l		X													

Visits	Screening		Randomization		Treatment period										Follow-up
	1 Step-1 ^a	1 Step-2 ^b	2 Step-1 ^c	2 Step-2 ^d	3	4	5	6	7	8	9	10	11	12 EOT ^g	13 EOS
Traditional group	Ⓞ (Digital screening)		☎	P	☎	☎	☎	P	☎	P	☎	P	☎	P	☎
Virtual group			☎	P & Ⓞ	Ⓞ	Ⓞ	Ⓞ	Ⓞ	Ⓞ	Ⓞ	Ⓞ	Ⓞ	Ⓞ	Ⓞ	Ⓞ
Weeks	-3	-2	-1	0	1	2	3	4	6	8	12	16	20	24	1 week
Window (day)			-/+ 4		-/+ 3	-/+ 3	-/+ 3	-/+ 4	-/+3	-/+ 4	-/+ 3	-/+ 4	-/+ 3	-/+ 3	+/-2
Urine analysis ^m		X													
Pregnancy test (WOCBP only) ⁿ		X		X				X		X		X		X	
PROs and other questionnaires^o															
Diabetes related PROs: DTSQs, DDS, HFS-II				X										X	
Diabetes related PRO: DTSQc														X	
Was it Worth It (WIWI) Questionnaire														X	
Work Productivity and Impairment Study Participation (WPAI-SP)				X										X	
Overall Study Experience - Participation (OSEP) part 1				X										X	
Overall Study Experience - Participation (OSEP) part 2														X	
Resource Use Questionnaire (RUQ)				X			X		X	X	X	X	X	X	
Overall Study Experience - Sites (OSES) – part 1 (resource requirements)				X	X	X	X	X	X	X	X	X	X	X	
Overall Study Experience – Sites (OSES) – part 2 (relationship, satisfaction)														X	
Qualitative exit interview ^p														X	

^a Prior to Visit 1, patients will be contacted by the sites or guided by the multi-channel digital recruiters to the eConsent web portal (Parallel 6 Website). Informed consent process will be completed electronically by the candidate trial patients. During the eConsent process, the study purpose, virtual tools for participation, and other protocol requirements will be introduced and discussed with the patients in the text or audio/video manner. After eSigning and counter-eSigning by the patient and the investigator, the enrolment IRT call will be made and the patient ID assigned.

- b* Assessments at Visit 1- Step 2 will be performed in-person by Homecare health professional (The MRN) in corporation with the study investigators and designees. This visit can occur at the patient's home, at work, or at any location providing the adequate space and level of privacy. Patient identification will be further verified and confirmed.

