- c* At the end of screening, investigators will determine the eligibility of the screened patients for participation. The randomization IRT call will be made at the Visit 2- Step 1. Patients will be informed by the study sites of their randomization group and Visit 2- Step 2 will be scheduled for the baseline assessments within 1 week (+/- 4 days).
Glucose meters with Bluetooth access and associated accessories (lancet, control solutions, test strips, etc), e-diaries features, and instructions will be shipped to all eligible patients. Patients will use the study provided glucose meters throughout the study.
- d* Physical examination will be performed at the in-person visit in the traditional group. In the virtual group, physical examination will be performed on-site, in-person, between randomization IRT call and the first IMP administration. All other assessments will occur remotely on the day of the first IMP administration (Day 1).
- e* Only for patients randomized in virtual group:
- They will receive the Bluetooth devices for their remote participation and the IMP (Toujeo®) before Visit 2-Step 2.
 - Shortly after randomization (IRT call), they will be scheduled for an in-person visit to allow for the initiation physical examination performed by the investigator.
 - They will be further trained on the Bluetooth devices utilization.
 - The IMP starting date and dose will be instructed by the investigator at the time of Visit 2-Step 2. The first IMP (Day 1) data will be documented with the dose in the e-CRF.
 - All study assessments, including vital signs and weight, will be done via the Bluetooth devices by the patients at home.
 - Patients located in the United States (US) will receive a laboratory requisition and have their blood drawn at any local Quest®. For patients located in Canada, blood draw will be performed by the Homecare via The MRN.
 - Unscheduled on-site visits or Homecare physician visits (depending on the patient's location) only for safety assessment could be scheduled as deemed necessary by the investigator (ie, performance of physical examinations is critical to determine a diagnosis or further evaluation procedure for an AE).
- f* IMP dose will be titrated at the investigator's discretion to achieve the fasting glycemic target while avoiding hypoglycemia

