8.1.5 Starting dose of investigational medicinal product

After randomization, patients will follow the investigator's instruction to start the IMP (Toujeo) and the daily dose of Toujeo at Visit 2-Step 2.

Patients randomized in the virtual group will receive the IMP by DTP process ([Section 8.1.3](#)) while patients in the traditional group will receive their IMP at the site at Visit 2-Step 2. The IMP should **NOT** be started until the completion of all the baseline performances (see flowchart in [Section 1.2](#)) and discussed with the investigator at Visit 2-Step 2, which should occur 7 (\pm 4) days after the randomization interactive response technology (IRT) call.

The starting dose of IMP on Day 1 is the patient's current insulin glargine 100 U/mL dose, ie, the same dose used on the day before. Patient should administer Toujeo at the same time of the day as their previous insulin glargine 100 U/mL injection, which is usually in the morning or in the evening around the same time daily.

Patient should not change the injection time during the 24-week treatment period.

The date, time, and dose of Toujeo will be documented in the e-CRF.

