10 STUDY PROCEDURES

This is an approximately 28-week outpatient study. Screening procedures will be performed as a virtual visit followed by a Homecare in-person visit. Eligible and consenting patients will be randomized to an approach group at telephone Visit 2-Step 1, which will determine the way the next visits are organized:

- Traditional group: 5 onsite visits and 7 telephone visits
- Virtual group: 11 virtual visits and 1 mixed onsite-virtual visit (Visit 2-Step 2)

Additional, optional virtual or telephone visits (according to the approach group) will be scheduled to monitor and support the progress of insulin titration whenever considered necessary by the investigator. For both groups, unscheduled onsite visits or Homecare physician visits (depending on the patient's location) may be scheduled only for safety assessment if deemed necessary by the investigator (ie, performance of physical examinations is critical to determine a diagnosis or further evaluation procedure for an AE).

All onsite visits should take place in the morning at approximately the same time. On the day before each onsite visit, patients should be reminded to bring the medical devices (glucose meter), diaries and IMP (used, in-use or unused) to sites and to be in the fasted status if required at some visits.

The **fasting condition** is defined as an overnight fast no less than 8 hours that consisted of no food or liquid intake, other than water. IMP and noninsulin antidiabetic medication should be administered after the fasting blood sample is drawn for all laboratory tests.

Note: If the patient is not in fasting conditions at visits which required in fasting conditions, the blood sample is not collected and a new appointment should be given to the patient for the following day if possible, with instruction to be fasted.

For phone-call visits and virtual visits, the patient is called by the investigator or qualified designee at a scheduled time.

A visit window of ± 3 days using the day of Visit 2-Step 2 as reference is acceptable (4 days for Visit 6, Visit 8, and Visit 10).

If one visit date is changed, the next visit should take place according to the original schedule, ie, counting from Day 1 on Visit 2-Step 2.

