11.4.3.3.1 Analysis of investigator questionnaires

For OSES ([Section 9.2.3.1](#)) a descriptive summary will be provided for each approach group at each applicable visit.

For OSES part 1 (study-specific resource requirements), a descriptive summary will be provided for each approach group at each applicable visit, and a total time will be calculated for each patient and averaged within each approach group. Overall Study Experience-Sites part 1 scores will be compared between approach groups using an ANCOVA. This model will include fixed categorical effects of approach group, on randomization strata of screening HbA1c ($<7.6\%$, $\geq 7.6\%$) and randomization strata of sites as well as continuous fixed covariates of corresponding baseline score.

For OSES part 2 (relationship and satisfaction), a descriptive summary will be provided for each item for each approach group at Week 24. Item scores will be compared between approach groups using an ANOVA. This model will include fixed categorical effects of approach group, on randomization strata of screening HbA1c ($<7.6\%$, $\geq 7.6\%$) and randomization strata of sites.

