2.4.7.6 Investigator (clinician) reported outcome (ClinRO) endpoints

Overall Study Experience-sites (OSES) questionnaire

For OSES Part 1 (study-specific resource requirements), a descriptive summary will be provided for each approach group at each applicable visit, and a total time will be calculated for each patient and averaged within each approach group. Overall Study Experience-Sites Part 1 scores will be compared between approach groups using the same approach as the one used for primary endpoint (MMRM model) as described in [Section 2.4.4.1.1](#). This model will include fixed categorical effects of approach group, on randomization strata of screening HbA1c (<7.6%, $\geq 7.6\%$) and randomization strata of sites as well as continuous fixed covariates of corresponding baseline score.

For OSES Part 2 (relationship and satisfaction), a descriptive summary will be provided for each item for each approach group at Week 24. Item scores will be compared between approach groups using an ANOVA. This model will include fixed categorical effects of approach group, on randomization strata of screening HbA1c (<7.6%, $\geq 7.6\%$) and randomization strata of sites.

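### The OSES Part 1 baseline covariate is measured after randomisation, at a visit already run under the assigned approach, so the adjusted difference in site time can shift

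*SAP*

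**What the plan says.** **Endpoint.** OSES Part 1 is one item: the time the investigator spent with the participant at the visit concerned (protocol 9.2.3.1, SAP 2.1.8). The synopsis lists "Overall Study Experience-Sites (OSES) questionnaire part 1 (resource requirements) over the 24 week treatment period".

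**Model.** Protocol 11.4.3.3.1: "Overall Study Experience-Sites part 1 scores will be compared between approach groups using an ANCOVA". SAP 2.4.7.6: "Overall Study Experience-Sites Part 1 scores will be compared between approach groups using the same approach as the one used for primary endpoint", meaning the MMRM of SAP 2.4.4.1.1. The SAP then lists approach, HbA1c stratum "and randomization strata of sites as well as continuous fixed covariates of corresponding baseline score", and the protocol lists the same terms. SAP 1.5 and 1.6, where a change from the protocol would be declared, are both marked not applicable.

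**Timing.** Randomisation is at telephone Visit 2-Step 1 (protocol 10 and 10.1.2.1). Footnote c of the flow chart: "Patients will be informed by the study sites of their randomization group and Visit 2- Step 2 will be scheduled for the baseline assessments". Protocol 8.1.5 puts Visit 2-Step 2 at 7 (±4) "days after the randomization interactive response technology (IRT) call". Protocol 10.1.2.2 makes that visit onsite for the traditional group and part onsite, part virtual for the virtual group. The OSES Part 1 row of the flow chart is marked at Visit 2-Step 2 and Visits 3 to 12, and nowhere earlier. Protocol 11.4 ties baseline to the first injection, not to randomisation, and SAP Table 2 labels Visit 2-Step 2 as Day 1.

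**What will be produced.** SAP section 2 records that the trial stopped with 15 patients randomised and that only basic descriptive statistics follow. SAP 2.5.4 assigns OSES forms to visits by date of data collection, using Table 2.

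**The concern.** A baseline covariate is safe when allocation cannot have altered it. The HbA1c baseline meets that condition because it comes from the screening sample. The OSES Part 1 baseline does not. It is the outcome itself, site time, measured at the first visit conducted under the assigned approach. Borrowing the structure of the primary model does not bring that model's validity with it. If the approach changes site time at Visit 2-Step 2, conditioning on that time changes the estimated difference at later visits.

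At stake is the comparison of site workload, which the protocol introduction gives as one reason for a virtual approach. The two documents also name different models for the same endpoint. Separately, the descriptive tables that will be produced depend on visit-assignment rules that do not match the visit schedule.

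**Working it through.** **1. The plan's own figure.** There is none for OSES Part 1: no minutes, SD or correlation. The only planning figure is the HbA1c precision (protocol 11.1, SAP 1.3). With 75 × 0.90 = 67.5 evaluable per arm, 1.96 × 1.1 × √(2/67.5) = 0.371, which matches the stated 0.37 for the between-approach difference. It is used here only to set the number per arm in step 4.

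**2. Is any pre-randomisation score planned?** The sequence is:
- Visit 1: no OSES entry.
- Visit 2-Step 1: randomisation, no OSES entry.
- Visit 2-Step 2, 3 to 11 days later (7 − 4 to 7 + 4): first OSES entry.

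The Day 1 window in Table 2 opens at Day −28, and SAP 2.1.8 speaks of every study visit. No form is scheduled before Visit 2-Step 2, however, so that window has nothing earlier to pick up.

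**3. Effect of adjustment.** Let D be the difference (virtual minus traditional) in later site time, d0 the difference at Visit 2-Step 2, and b the common within-arm slope of later time on Visit 2-Step 2 time. Then:

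adjusted difference = D − b·d0

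| Situation | Adjusted difference |
|---|---|
| d0 = 0 or b = 0 | unchanged |
| b·d0 has the sign of D and is smaller in size | attenuated |
| b·d0 has the sign of D and is larger in size | sign reversed |
| b·d0 has the opposite sign to D | inflated |
| D = 0, b·d0 not 0 | spurious difference |

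**4. Check with assumed inputs.** Units are SDs, and SDs are taken as equal so that b is the correlation. All values are assumptions. The simulation used 67 per arm, six sites, the HbA1c stratum and 2,000 runs, with a single-outcome ANCOVA standing in for the MMRM. Each cell gives formula / simulated mean.

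| D | d0 | b = 0.3 | b = 0.5 | b = 0.7 |
|---|---|---|---|---|
| −0.5 | 0 | −0.50 / −0.506 | −0.50 / −0.498 | −0.50 / −0.500 |
| −0.5 | −0.5 | −0.35 / −0.353 | −0.25 / −0.251 | −0.15 / −0.150 |
| −0.5 | +0.5 | −0.65 / −0.650 | −0.75 / −0.748 | −0.85 / −0.851 |
| 0 | −0.5 | +0.15 / +0.150 | +0.25 / +0.246 | +0.35 / +0.351 |

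A reversal, by formula only: D = −0.5, d0 = −1.0, b = 0.7 gives −0.5 + 0.7 = +0.2. Without the covariate, the simulated mean stays within 0.01 of D in every row.

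**5. Table 2 against the visit schedule.** Visit days are counted from Visit 2-Step 2 as Day 1.

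| Visit | Allowed days | OSES Part 1 window |
|---|---|---|
| 5 (Week 3) | 22 ± 3 = 19–25 | 19–25 |
| 6 (Week 4) | 29 ± 4 = 25–33 | 26–32 |
| 7 (Week 6) | 43 ± 3 = 40–46 | 36–49 |

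A Visit 6 form dated Day 25 goes to Week 3, and one dated Day 33 has no window. The Day 1 window closes on Day 1 and Week 1 opens on Day 5, so a Visit 2-Step 2 form entered on Days 2–4 has no window. If the first dose falls on the day after Visit 2-Step 2, all study days drop by one: Visit 6 covers Days 24–32, and Days 24 and 25 go to Week 3. The mismatch changes form but does not disappear.

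OSES Part 1 also appears in two blocks. Week 24 is Days 141–196 in one and 155–196 in the other. A Visit 11 form on Days 141–144, inside its allowed 138–144, is Week 24 in the first block and Week 20 in the second.

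**6. Who completes the form.** Protocol 10.1.2.2 places OSES Part 1 among questionnaires that traditional-group patients fill in during the week before the site visit. Protocol 9.2.3.1 and 10.1.4 and SAP 2.1.8 assign it to the investigator, and 9.2.3.1 and SAP 2.1.8 place it after the visit. The conflicting entry creates no pre-randomisation value, because it applies to a group that exists only once patients are randomised.

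**The case against.** The strongest reply is lack of consequence. The model will not be run on the 15 patients, the endpoint is one of many secondary ones, and its intervals are descriptive. This stands, and it sets the severity.

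The by-visit summaries by approach would also show any Visit 2-Step 2 difference to a careful reader. That is true, but the planned adjusted estimate would still be D − b·d0, and neither document justifies the covariate or plans an analysis without it.

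The covariate buys precision, and an unadjusted sensitivity analysis could sit beside it. That would expose the shift. It would still leave, as the main estimate, one conditioned on something allocation may have changed.

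Several stronger readings are tempting but not supported:

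- A reader might infer that adjustment always shrinks the difference. Steps 3 and 4 show that it can equally inflate it, reverse it or create one.
- A reader might infer a direction from the virtual group's extra onsite examination. The documents give no site times, so neither size nor sign follows.
- A reader might take the 13 days without a window (2–4, 33–35, 64–70: 3 + 3 + 7) as a large expected loss. With Visit 2-Step 2 on Day 1, the only such day that an on-schedule, promptly completed form reaches is Day 33. The rest need late entry or an out-of-window visit.
- A reader might treat the two OSES Part 1 blocks as a deliberate double rule. The first block has only Day 1 and Week 24, which is the OSEP Part 1 schedule, and OSEP Part 1 has no row. A slip is the likelier explanation, for the sponsor to confirm.

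**Conclusion.** The concern holds, at minor severity. The OSES Part 1 baseline is a post-randomisation measurement of the outcome, and using it as a covariate can move the adjusted difference by −b·d0. There is no shift only if mean site time at Visit 2-Step 2 is equal in the two arms or unrelated to later time. The figures in step 4 confirm the formula under assumed inputs and a common slope; they do not estimate the shift in this trial.

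The documents do not support saying that any result of this trial is biased by the model, because SAP section 2 replaces it with descriptive output. The model point therefore applies to the protocol and SAP text and to any later study that reuses it. The ANCOVA/MMRM disagreement is a plain inconsistency. The Table 2 mismatches and the conflict over who completes the form do bear on the descriptive tables for the 15 patients, though probably for few forms.

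**What to change.** **Model text (protocol 11.4.3.3.1 and SAP 2.4.7.6).** State one model and record the change in SAP 1.5 or 1.6. Remove the OSES Part 1 baseline score. Keep approach, site and HbA1c stratum, and add visit and approach-by-visit if the MMRM is retained. Report Visit 2-Step 2 time by approach as a post-randomisation result, not as a baseline.

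**SAP Table 2.** Align the OSES Part 1 windows with the allowed visit days, so that Visit 6 forms on Days 25 and 33 go to Week 4. Give Visit 2-Step 2 forms entered on Days 2–4 a window. Keep a single OSES Part 1 block, and confirm whether the first block was meant for OSEP Part 1.

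**Respondent.** Reconcile protocol 10.1.2.2 with protocol 9.2.3.1 and 10.1.4 and SAP 2.1.8.

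**Cost.** Wording and derivation rules only; no new data. Dropping the covariate widens the confidence interval by an amount that depends on the unknown visit-to-visit correlation. In the check above with d0 = 0, the standard error was 0.172 SD without the covariate, against 0.165, 0.150 and 0.124 with it at assumed correlations of 0.3, 0.5 and 0.7. For the 15 randomised patients only the Table 2 and respondent corrections, and the labelling of Visit 2-Step 2, have any effect.

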2.4.8 Patient interviews

Exit interviews with a subset of patient from the virtual group is described in [Section 2.1.10](#). Data will be analyzed via an expert qualitative research analysis group using standardized qualitative methods (eg, thematic analysis, grounded theory). No details of analysis will be provided in this SAP, but will be developed by expert.

2.5 DATA HANDLING CONVENTIONS

2.5.1 General conventions

The following formulas will be used for computation of parameters.

Reference day

The reference day for the calculation of extent of exposure, time to onset and relative days is the day of the first administration of IMP, denoted as Day 1.

Demographic formulas

Body Mass Index (kg/m^2) = (Weight in kg)/(Height in meters)².

Disease characteristics formulas

Duration of diabetes (years) = (Date of informed consent – date of diagnosis of diabetes +1)/365.25.

Age at onset of diabetes (years) = (Date [DD-MM-YYYY] of diagnosis of diabetes – date [DD-MM-YYYY] of birth +1) /365.25. In case of unavailable date of birth, only the year of the date of diabetes diagnosis and the year of the date of birth (retrieve using the age recorded at screening) will be considered in the age at onset calculation.

Duration of previous mealtime insulin treatment (years) = Duration of mealtime insulin treatment in patient life (years) = (Date of informed consent – Date of first intake of mealtime Anti-hyperglycemic therapy in patient life +1)/365.25.

Duration of basal insulin treatment (years) = (Date of informed consent – Date of first intake of Basal Anti-hyperglycemic therapy +1)/365.25

HbA1c transformation

To transform HbA1c in % to mmol/mol, the following formula is used:

$$\text{IFCC} = (10.93 \times \text{NGSP}) - 23.50$$

NGSP (National Glycohemoglobin Standardization Program network) corresponds to HbA1c (%) and IFCC (International Federation of Clinical Chemistry network) to HbA1c (mmol/mol)

FPG and SMPG conversion

From mg/dL to mmol/L: x 0.0555

From mmol/L to mg/dL: x 18.0148

Renal function formulas

Conversion for serum creatinine:

From mg/dL to $\mu\text{mol/L}$: x 88.402

Conversion for total bilirubin:

From mg/dL to $\mu\text{mol/L}$: x 17.104

Creatinine clearance (CL_{Cr}) value will be derived using the equation of Cockcroft and Gault (2), using weight assessed at the same visit:

- For Male:

$$\text{CL}_{\text{Cr}} (\text{mL/min}) = \frac{[(140 - \text{age}(\text{years})) \times \text{weight}(\text{ kg})]}{[0.814 \times \text{serum creatinine} (\mu\text{mol/L})]}$$

- For Female: result above multiplied by 0.85.

eGFR will be derived using MDRD formula (3):

$$eGFR \text{ (mL/min/1.73m}^2\text{)} = \left[\begin{array}{l} 175 \times \text{Serum Creatinine (mg/dL)}^{-1.154} \times \text{Age}^{-0.203} \times 1.212 \text{ (if black)} \\ \times 0.742 \text{ (if female)} \end{array} \right]$$

